## **1.4.2.** Potential Benefits

At this stage in VC-02 clinical development, there are no known benefits. However, there are several potential benefits of this therapy as noted below.

- Improved overall glycemic control
- Reduction in exogenous insulin dosing
- Reduction in the number of insulin injections and/or complete elimination of exogenous insulin injections
- Reduction in the frequency of blood glucose monitoring
- Reduction in the number of hypoglycemic events
- Improvement in hypoglycemia awareness (Leitao, et al., 2008)
- Reduction in the risk of micro- and macro-vascular complications
- Improvement in Quality of Life from an economic and lifestyle standpoint (e.g., decreased exogenous insulin requirements, fewer self-monitoring blood glucose supplies, dietary freedom)

The allowed number of VC-02 units implanted in Cohort 2 is higher than the allowed number of units implanted in Cohort 1. While subjects enrolled in Cohort 2 will have a higher likelihood of experiencing clinical benefit, it is possible subjects in Cohort 1 may experience some degree of clinical benefit as well.

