### 2.2.2. Secondary Endpoint Measures

Secondary Safety and Tolerability Endpoints: The comprehensive safety profile of VC-02 combination product implanted for up to two years as measured by:

- All reported AEs
- The incidence of immune sensitization defined by presence of donor anti-HLA antibodies absent prior to implant.
- Implant tolerability assessments (e.g., fever, erythema, pain, tenderness, induration) for up to four hours post-implantation and at subsequent visits.
- The incidence of subjects requiring a premature explant due to safety, tolerability, or malfunction issues.

Secondary Efficacy Endpoints:

- Change from baseline to Weeks 16, 26, 39, 52, 78, and 104 in C-peptide AUC0-2h or AUC0-4h following an MMTT;
- Time to onset of biological response of C-peptide following MMTT;
- Percent of subjects achieving a positive stimulated C-peptide (defined as >0.2 ng/mL) after implant;
- Change from baseline to Weeks 16, 26, 39, 52, 78, 104 in weekly frequency of hypoglycemic events;
- Percent of subjects free of severe hypoglycemic events from Week 16 to Weeks 20, 26, 39, 52, 78, and 104;
- Change from baseline to Weeks 16, 26, 39, 52, 78 and 104 in Clarke score;
- Change from baseline to Weeks 16, 26, 39, 52, 78, and 104 in average daily insulin dose in the seven days preceding the Clinic Visits;
- Percent of subjects who achieve a 50% reduction in average weekly exogenous insulin dose from baseline to Weeks 16, 20, 26, 39, 52, 78, and 104;
- Percent of subjects who achieve exogenous insulin independence; of those subjects achieving insulin independence, the percent achieving HbA1c <7.0%
- Percent of time spent with blood glucose values at various cut points (e.g., <54 mg/dL, ≥54 to <70 mg/dL, ≥70 mg/dL to ≤180 mg/dL, and >180 mg/dL) as measured by each subject's CGM device.

• Change from baseline to Weeks 16, 26, 39, 52, 78, and 104 in time-in-euglycemic range (≥70 mg/dL to ≤180 mg/dL), time-in-hypoglycemic ranges (<54 mg/dL and ≥54 to <70 mg/dL), and time-in-hyperglycemic ranges (>180 mg/dL) as measured by each subject's CGM

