#### Secondary Efficacy Endpoints:

#### *VC02-101*:

- Change from baseline to Weeks 8, 12, 16, 20, 26, 39, 52, 65, 78, 91, and 104 in C-peptide area under the curve from 0 to 2 hours (AUC0-2h) or AUC0-4h following an MMTT;
- Time to onset of biological response of C-peptide following MMTT;
- Percent of subjects achieving a positive stimulated C-peptide (defined as >0.2 ng/mL) after implant;
- Change from baseline to Weeks 16, 26, 39, 52, 78, 104 in weekly frequency of hypoglycemic events;
- Percent of subjects free of severe hypoglycemic events between study visits starting with Week 16 (i.e., Weeks 16-20, Weeks 20-26, Week 26-39, Weeks 39-52, Weeks 52-65, Weeks 65-78, Weeks 78-91, Weeks 91-104);
- Percentage of subjects free of severe hypoglycemic events between Week 16 and Week 104 (or early termination).
- Change from baseline to Weeks 16, 26, 39, 52, 78 and 104 in Clarke score;

- Change from baseline to Weeks 16, 26, 39, 52, 78, and 104 in average daily insulin dose;
- Percent of subjects who achieve a 50% reduction in average weekly exogenous insulin requirements from baseline to Weeks 16, 20, 26, 39, 52, 78, and 104;
- Percent of subjects who achieve exogenous insulin independence;
- Percent of time spent with blood glucose values at various cut points (e.g., <54 mg/dL, ≥54 to <70 mg/dL, ≥70 mg/dL to ≤180 mg/dL, >180 mg/dL, and >250 mg/dL) as measured by each subject's continuous glucose monitoring (CGM) device.
- Change from baseline to Weeks 16, 26, 39, 52,78, and 104 in time-in-euglycemic range (≥70 mg/dL to ≤180 mg/dL), time-in-hypoglycemic ranges (<54 mg/dL and ≥54 to <70 mg/dL), and time-in-hyperglycemic ranges (>180 mg/dL and > 250 mg/dL) as measured by each subject's CGM.

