#### 4.6.6.1 Daily and Weekly Exogenous Insulin Dose

Baseline average daily and average weekly exogenous insulin dose requirements will be calculated using up to 28 days of data. Baseline average daily and average weekly insulin requirements will be calculated using data starting at Day -3 (i.e., the day prior to immunosuppression induction) and working backwards for up to 28 days (through Day -30). For instances in which the available pre-implant dataset provides <28 days of data, the dataset will be supplemented with post-implant data, using data from Day 4 forward until 28 days of data is available. Data from days on which an MMTT or SOGCT was performed, will not be included in the calculation.

At Weeks 16, 26, 39, 52, 78, and 104, the last 7 daily total exogenous insulin doses recorded in the log will be used to calculate the average daily and the average weekly exogenous insulin dose at that visit. The last 7 daily records must be within the previous 14 calendar days and may not include a day in which an MMTT or SOGCT was performed. There must be at least 4 days worth of data for a particular timepoint to be considered evaluable. The weekly average value will be calculated as:

7 \* (sum of the insulin doses during the period / number of days with insulin doses in the period).

In each period, subjects must have four different days with recorded exogenous insulin doses in order for the value to be calculated.

The percent reduction in average weekly exogenous insulin dose from baseline at these visits will be calculated as:

(Average weekly insulin dose at post-baseline visit - baseline average weekly insulin dose)\*100/ baseline average weekly insulin dose.

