The number and percent of subjects free of severe hypoglycemic events between study visits (Weeks 16-20, Weeks 20-26, ..., Weeks 91-104, and Weeks 16-104) will each be analyzed using Fisher's exact test. The number and percent of subjects in each treatment group and the p-value from the Fisher's test will be provided (at each time point, where appropriate). These analyses will be performed using both HEs from patient-reported diary and HEs from CGM.

Change from baseline to Weeks 16, 26, 52, 78 and 104 in Clarke score will be analyzed using ANCOVA, with treatment group as a factor and the relevant baseline as a covariate. A listing of the Clarke total score will be provided.

Change from baseline to Weeks 16, 26, 39, 52, 78 and 104 in average daily insulin requirement in the seven days preceding the clinic visit will be analyzed using ANCOVA, with treatment group as a factor and the relevant baseline as a covariate. A listing of insulin dosing will be provided.

The number and percent of subjects who achieve a 50% reduction in average weekly exogenous insulin dose from baseline to Weeks 16, 20, 26, 39, 52, 78, and 104 will each be analyzed using Fisher's exact test. The number and percent of subjects in each treatment group and the p-value from the Fisher's test will be provided (at each time point, where appropriate).

The number and percent of subjects who achieve exogenous insulin independence (both definitions will each be analyzed using Fisher's exact test. The number and percent of subjects in each treatment group and the p-value from the Fisher's test will be provided (at each time point, where appropriate).

Percent of time spent with blood glucose values at various cut points at each scheduled visit will be summarized descriptively. The coefficient of variation (CV) of blood glucose values will be included in the summary. The percentages and change from baseline percentages will be summarized for each cut point (<54 mg/dL,  $\geq$ 54 to <70 mg/dL,  $\geq$ 70 mg/dL to  $\leq$ 180 mg/dL,  $\geq$ 180 mg/dL, and >250 mg/dL) and for each treatment group. The number of subjects with Prolonged HEs (duration > 120 minutes for cut points  $\leq$ 54 mg/dL and  $\leq$ 70 mg/dL) will also be summarized.

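### SAP 4.6.6.1 labels a percent-change formula as percent reduction, and neither document states a sign or cut-off for the 50% insulin-reduction responder endpoint

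*SAP*

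**What the plan says.** **Derivation.** SAP 4.6.6.1 introduces the quantity with "The percent reduction in average weekly exogenous insulin dose from baseline at these visits will be calculated as" and then gives a numerator of "Average weekly insulin dose at post-baseline visit - baseline average weekly insulin dose", times 100, over the baseline average weekly dose. It defines no responder rule.

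**Endpoint and analysis.** The protocol (2.2.2) lists "Percent of subjects who achieve a 50% reduction in average weekly exogenous insulin dose from baseline to Weeks 16, 20, 26, 39, 52, 78, and", the series closing with Week 104. The SAP's endpoint list (2.2.2, VC02-101) has the same endpoint and the same weeks, with requirements in place of dose. SAP 6.2 analyses "The number and percent of subjects who achieve a 50% reduction in average weekly exogenous insulin dose" by treatment group with Fisher's exact test, as does protocol 10.4.5.1. None of these sections says whether the threshold is at least 50 or at most −50, or whether an absolute value is taken. The protocol gives no formula, so SAP 4.6.6.1 is the only derivation.

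**Direction of benefit.** Protocol 1.4.2 lists "Reduction in exogenous insulin dosing" among the potential benefits.

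**Visits.** SAP 4.6.6.1 derives the dose as follows: "At Weeks 16, 26, 39, 52, 78, and 104, the last 7 daily total exogenous insulin doses recorded in the log will be used". Week 20 is not in that list, and the percent-reduction formula is tied to the same visits.

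**The concern.** The label and the formula have opposite signs. A quantity called percent reduction should be positive when the dose goes down; this one is negative. The endpoint is worded as a reduction of 50%, so the most direct way to program it is to derive the named quantity and compare it with 50. Doing that would flag the wrong subjects.

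At stake are the responder counts and percentages for one efficacy endpoint at up to seven visits. Those counts are the reported result whether or not a p-value is attached. SAP 4.1 has each program checked against its specification. A specification that copied 4.6.6.1 would carry the sign error with it, and a program that followed it would pass. Even if responders were flagged correctly, a table headed percent reduction would show improvements as negative numbers.

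**Working it through.** **Inputs.** The formula is from SAP 4.6.6.1. The 50% threshold is from SAP 2.2.2 and 6.2 and protocol 2.2.2. The documents give no worked example or dose figures to reproduce. The baseline of 280 units per week used below is an assumption for illustration; the result depends only on the ratio of post-baseline to baseline dose.

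**Formulas.** Let b be the baseline weekly dose and p the post-baseline weekly dose.

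- As printed: S = (p − b) × 100 / b
- True reduction: R = (b − p) × 100 / b = −S

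**Thresholds in terms of the ratio p/b.**

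- S ≥ 50 means p/b − 1 ≥ 0.5, so p/b ≥ 1.5.
- R ≥ 50 means 1 − p/b ≥ 0.5, so p/b ≤ 0.5.
- S ≤ −50 means p/b ≤ 0.5, the same subjects as R ≥ 50.

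**Values with b = 280 (assumed).**

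| p (units/week) | p/b | S, as printed | R, true reduction | S ≥ 50 | R ≥ 50 | S ≤ −50 |
|---|---|---|---|---|---|---|
| 0 | 0 | −100 | +100 | no | yes | yes |
| 70 | 0.25 | −75 | +75 | no | yes | yes |
| 140 | 0.50 | −50 | +50 | no | yes | yes |
| 141 | 0.504 | −49.64 | +49.64 | no | no | no |
| 210 | 0.75 | −25 | +25 | no | no | no |
| 280 | 1.00 | 0 | 0 | no | no | no |
| 350 | 1.25 | +25 | −25 | no | no | no |
| 419 | 1.496 | +49.64 | −49.64 | no | no | no |
| 420 | 1.50 | +50 | −50 | yes | no | no |
| 560 | 2.00 | +100 | −100 | yes | no | no |

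The set picked out by S ≥ 50 (ratio 1.5 or more) and the intended set (ratio 0.5 or less) do not overlap.

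**Check against a neighbouring definition.** SAP 4.6.6.2 counts a subject as insulin independent, under its first definition, after 14 consecutive days with a recorded dose of zero. If those days immediately precede a visit, the weekly average at that visit is 7 × (0/7) = 0 and S = −100. Under S ≥ 50 that subject would be insulin independent and yet fail the 50% reduction endpoint. The two definitions cannot both be meant on that reading.

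**Week 20, a separate check.**

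- Dose derived (SAP 4.6.6.1): Weeks 16, 26, 39, 52, 78, 104.
- Responder endpoint (protocol 2.2.2 and 10.4.5.1, SAP 2.2.2 and 6.2): Weeks 16, 20, 26, 39, 52, 78, 104.

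The only difference is Week 20. The data should exist, because the protocol requires daily insulin entries throughout participation (5.4.2, 7.10.1) and has a Week 20 visit (6.10). What is missing is the derivation rule.

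**The case against.** The strongest reply is that the reversal needs a rule the SAP does not contain. SAP 4.6.6.1 derives a continuous quantity; SAP 6.2 speaks of a 50% reduction in ordinary language, which means the dose fell by half, and that is −50 on the printed formula. A programmer who applies −50 or lower gets exactly the right subjects. The direction of benefit is unmistakable, a literal program would give absurd results for subjects on no insulin, and the planned listing of insulin dosing would help expose them.

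Much of this stands. A reader might infer that the plan as written reverses the responder endpoint. The documents do not support that: the reversal is conditional on comparing the derived value with +50, a cut-off stated nowhere. Nor would that comparison select everyone whose dose rose; a 25% rise computes as +25 and fails. A reader might also take this for a key endpoint. The documents give a single unranked list of secondary efficacy endpoints, call their p-values descriptive (protocol 10.4.5, SAP 6.2) and state that no hypotheses are tested (protocol 10.1, SAP 4.5).

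What the reply does not remove is the mismatch itself. The formula is legible and explicit, it contradicts its own label, and the correct result depends on the programmer noticing. Nor does it supply the missing cut-off: the text does not even say at least 50%.

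**Conclusion.** The point holds as a specification error. The quantity labelled percent reduction is percent change, and the responder endpoint that depends on it has no stated sign or inequality. If, and only if, the derived value is compared with +50, the responders are the subjects whose weekly dose rose by 50% or more, and those with a halved or zero dose are excluded. This rests on algebra and on the ratio alone; the 280-unit baseline is illustrative and says nothing about the size of any effect in this trial.

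The reach is limited to one secondary endpoint with descriptive p-values. The primary C-peptide analysis (SAP 6.1), the ANCOVA on change in average daily insulin (SAP 6.2) and both definitions of insulin independence (SAP 4.6.6.2) do not use the formula. The error should be corrected because it sits in the only derivation of a named efficacy endpoint and costs almost nothing to fix.

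The Week 20 gap is also real. It is a separate inconsistency and lends no weight to the sign error.

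**What to change.** In SAP 4.6.6.1, do one of the following, which select the same subjects:

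- Keep the label percent reduction, change the formula to (baseline − post-baseline) × 100 / baseline, and define a responder as a value of at least 50.
- Keep the formula, rename the quantity percent change, and define a responder as a value of −50 or lower.

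Refer to that rule from SAP 6.2 so that the cut-off is stated once and used in the analysis.

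Separately, add Week 20 to the visits in 4.6.6.1 for the weekly dose and the responder endpoint. The daily-dose ANCOVA in SAP 6.2 does not include Week 20 and need not change.

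The cost is a few short text edits to the SAP: formula or label, cut-off with cross-reference, and visit list. No new data collection is needed, and the sign correction needs no protocol change because the protocol gives no formula.

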## 4.6.6.2 Exogenous Insulin Independence

Exogenous insulin independence will be defined in two ways.

First, achieving exogenous insulin independence is defined as having an exogenous insulin dose of 0 for a minimum of any 14 consecutive days during the study, based on the data from exogenous daily insulin dose logs. Missing or blank values on the daily insulin log are not considered to be 0 values.

The second definition of exogenous insulin independence includes having an exogenous insulin dose of 0 for a minimum of any 14 consecutive days (the first definition of insulin independence) in addition to having HbA1c  $\leq$  7.0%, and (2-hour or 4-hour) MMTT fasting (at the start of the MMTT) glucose  $\leq$  125 mg/dL and 120-minute glucose  $\leq$  180 mg/dL. The HbA1c value and the MMTT glucose values will be those values obtained at a clinic visit that is closest temporally to the 14 consecutive days of 0 exogenous insulin dose. Depending on when the 0 doses of insulin begin, it is possible that the closest value temporally for HbA1c may be from a different clinic visit than the closest value temporally for glucose from the MMTT.

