## 10.4.5.1. Secondary Efficacy Analyses

The FAS will be used to analyze the secondary efficacy endpoints, with the analysis for each endpoint performed within each Cohort. Change from baseline in C-peptide  $AUC_{0-4h}$  following an MMTT at Weeks 52 and 104 and change from baseline in C-peptide  $AUC_{0-2h}$  following an MMTT at Weeks 16, 26, 39, 52, 78, and 104 will be analyzed in a similar manner to the ANCOVA performed for change from baseline in C-peptide  $AUC_{0-4h}$  at Week 26, with the relevant baseline as the covariate.

Change from baseline in frequency of hypoglycemic events (24-hour; daytime [start between 6 a.m. - 12 a.m.]; nocturnal [start between 12 a.m. - 6 a.m.]) at Weeks 16, 26, 52, 78; change from baseline to Weeks 16, 26, 52, 78 and 104 in Clarke score; and change from baseline to Weeks 16, 26, 52, 78 and 104 in average daily insulin dose in the seven days preceding the clinic visit will be analyzed using ANCOVA, with treatment group as a factor and the relevant baseline as a covariate.

Time to onset of biological response of C-peptide following MMTT will be assessed using Kaplan-Meier (KM) curves, with the p-value from the logrank test also provided.

The percent of subjects achieving a positive stimulated C-peptide (defined as > 0.2 ng/mL) after implant; the percent of subjects free of severe hypoglycemic events from Week 16 to Weeks 20, 26, 39, 52, 78 and 104; the percent of subjects who achieve a 50% reduction in average weekly exogenous insulin dose from baseline to Weeks 16, 20, 26, 39, 52, 78, and 104; the percent of subjects who achieve exogenous insulin independence; the percent of subjects who achieve exogenous insulin independence and an HbA1c < 7.0% will each be analyzed using Fisher's exact test. The number and percent of subjects in each treatment group and the p-value from the Fisher's test will be provided (at each timepoint, where appropriate).

Percent of time spent with blood glucose values at various cut points at each scheduled visit will be summarized descriptively. The percentages and change from baseline percentages will be

summarized for each cut point (<54 mg/dL,  $\geq$ 54 to <70 mg/dL,  $\geq$ 70 mg/dL to  $\leq$ 180 mg/dL, and >180 mg/dL) and for each treatment group.

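### The SAP replaces the protocol's HbA1c result for insulin-independent subjects with a composite that adds two glucose limits, and so plans no HbA1c-only result

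*SAP*

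**What the plan says.** - **Protocol 2.2.2** (with the same wording in the Protocol Summary) lists insulin independence and then "of those subjects achieving insulin independence, the percent achieving HbA1c <7.0" per cent. The denominator is the subjects who became independent.
- **Protocol 10.4.5.1** gives the analysis as the percent of subjects with "exogenous insulin independence and an HbA1c < 7.0% will each be analyzed using Fisher's exact test". It adds: "The number and percent of subjects in each treatment group and the p-value from the Fisher's test will be provided". It also fixes the analysis set: "The FAS will be used to analyze the secondary efficacy endpoints". The denominator is therefore all FAS subjects in the treatment group.
- **SAP 2.2.2** reduces the bullet to "Percent of subjects who achieve exogenous insulin independence". The HbA1c clause is not there.
- **SAP 4.6.6.2** gives two definitions. The first is a zero insulin dose on at least 14 consecutive days. Of the other it says: "The second definition of exogenous insulin independence includes having an exogenous insulin dose of 0 for a minimum of any 14 consecutive days". To that it adds HbA1c of 7.0% or less, "2-hour or 4-hour) MMTT fasting (at the start of the MMTT) glucose" of 125 mg/dL or less, and a 120-minute glucose of 180 mg/dL or less.
- **SAP 6.2** analyses both definitions with Fisher's exact test and reports number and percent per treatment group.
- **Protocol 10** (introduction) lets the SAP depart from the protocol, but major changes to endpoints or their analyses are to appear in a protocol amendment. The SAP Revisions table has no entry that explains the missing HbA1c clause or the glucose limits.

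**The concern.** The protocol endpoint asks a plain question: when subjects come off insulin, is their HbA1c at target? The SAP's second definition asks a stricter one. A subject who stops insulin, reaches the HbA1c target and then has a 120-minute glucose above 180 mg/dL is a success under both protocol sections and a failure under the SAP.

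The added limits are a real restriction. Protocol 7.2 allows the MMTT to start at any fasting glucose from 70 to 200 mg/dL, so a valid test can fail the 125 mg/dL limit.

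At stake is whether the report can answer the protocol's question at all. There is also the lesser matter that an open-label trial with several unreconciled versions of an endpoint leaves room to choose one after the data are seen.

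**Working it through.** The documents state no expected rate or power for this endpoint, so there is no figure to reproduce. The check is proportion arithmetic on the versions as written.

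**Definitions.** Let π be the share of FAS subjects who become independent (SAP first definition), h the share of those at the HbA1c target, and g the share of those at target who also meet both glucose limits. All three are unknown.

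- A (Protocol 2.2.2) = h
- B (Protocol 10.4.5.1) = π × h
- C (SAP 4.6.6.2 and 6.2, second definition) = π × h × g

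Hence B/C = 1/g and A/B = 1/π.

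**Effect of the added glucose limits (assumed g).** B/C is 1/1.00 = 1.0 at g = 100%, 1/0.75 = 1.33 at 75%, and 1/0.50 = 2.0 at 50%.

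**Effect of the denominator (assumed π).** A/B is 10 at π = 10%, 5 at 20%, 2 at 50% and 1.25 at 80%. This holds whatever h and the sample size are.

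**Example with assumed counts.** Take 40 subjects (the number SAP 10 names for the optimized conditions), treated as one group: 12 independent, 9 of them at the HbA1c target, 5 of those within both glucose limits.

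| Version | Calculation | Result |
|---|---|---|
| A, Protocol 2.2.2 | 9/12 | 75% |
| B, Protocol 10.4.5.1 | 9/40 | 22.5% |
| C, SAP second definition | 5/40 | 12.5% |
| SAP first definition | 12/40 | 30% |

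Here g = 5/9 = 56% and B/C = 9/5 = 1.8.

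**Can the protocol result be recovered from the SAP tables?** They would give 12 and 5. The 9 lies between them and is not reported. From 12 and 5 alone, the number at the HbA1c target could be anything from 5 to 12. The joint percentage could then be anywhere from 5/40 = 12.5% to 12/40 = 30%, and the conditional one from 5/12 = 42% to 12/12 = 100%. Dividing the two SAP counts gives 42%, which is the conditional rate of the whole composite, not of HbA1c. HbA1c is otherwise planned as a laboratory value by visit, cohort and treatment group (SAP 7.3 and 7.3.5), not among independent subjects.

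**Cut-off.** The protocol uses below 7.0% and the SAP 7.0% or less, so a value of exactly 7.0% is classed differently. The ratios and ranges above ignore this.

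**The case against.** Several points on the other side stand.

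- A reader might infer that the reported percentage is wrong by several-fold because three denominators compete. The documents do not support that. There are two denominators and two component sets, and the large ratios are the identity 1/π between a conditional and a joint percentage. Under Protocol 10.4.5.1 alone, the counts for independence and for independence with HbA1c are both reported, so the conditional figure follows (9 out of 12 in the example). Only the step to the SAP composite loses information.
- A reader might infer that a low composite could simply hide how few subjects stopped insulin. It could not, because SAP 6.2 reports the first definition alongside it.
- A reader might infer that the SAP abandons HbA1c. It does not: HbA1c remains a component of the second definition and is a scheduled laboratory test.
- A reader might infer that Protocol 10.4.5.1 should move to the conditional denominator. That is not required. The joint percentage in the FAS is a legitimate basis for Fisher's test. Conditioning on independence compares subsets selected by a post-implant outcome and is undefined in a group where nobody becomes independent.
- Whether the change is major enough to need an amendment under Protocol 10 is a judgement. The SAP Revisions table covers only changes after SAP version 1.0, so its silence does not date the glucose limits. It shows only that no reason is given.

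The endpoint is secondary, its p-values are descriptive (Protocol 10.4.5, SAP 6.2), and no hypotheses are tested (Protocol 10.1). None of this supplies the missing HbA1c-only count.

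**Conclusion.** The concern holds as an alignment error of minor to moderate weight. As written, the SAP produces neither the conditional percentage of Protocol 2.2.2 nor the joint percentage of Protocol 10.4.5.1, and neither can be worked out from the two counts it does report. It cannot show whether subjects who stopped insulin missed the HbA1c target or only a glucose limit.

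The composite is lower than the protocol's joint percentage by the factor g: no difference at g = 100%, half at g = 50%. These are assumed values, and the size in this trial is unknown. The conditional and joint percentages differ by 1/π by construction. That is not an error, but each must carry its denominator.

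The primary endpoint, the type I error and the plain independence percentage are not affected.

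**What to change.** In SAP 2.2.2, 4.6.6.2 and 6.2, reinstate the protocol endpoint as a row of its own: the number of subjects who meet the first definition and have HbA1c below 7.0%. Show that number in two labelled ways:

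1. As a percent of insulin-independent subjects (Protocol 2.2.2), descriptive, with an exact confidence interval. The denominator may be small: 9 of 12 has an exact 95% interval of about 43% to 95%, which is a reason to print the count and interval.
2. As a percent of the FAS treatment group (Protocol 10.4.5.1), with Fisher's exact test.

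Keep the composite with glucose limits as a separately named additional endpoint and give its rationale. The denominator in Protocol 10.4.5.1 need not change.

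The cost is SAP wording and one more row in an existing table. HbA1c is already scheduled at Weeks 16, 26, 52, 78 and 104, so no new data are needed.

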### 7.2. Mixed Meal Tolerance Test (MMTT)

MMTTs are conducted after all other vital signs evaluations and laboratory tests have been collected. The MMTT test should only be started if the subject has been fasting for at least eight

(8) hours. All MMTT supplies will be provided by the Sponsor or designee. Basal exogenous insulin will be continued during the test, but any short-acting insulin will be withheld starting four hours prior to starting the test. Prior to initiating the MMTT, the subject's fasting glucose will be tested at the site and the value must be within 70-200 mg/dL to begin the MMTT. If the fasting glucose is not initially within range, the site may recheck levels while the subject is still at the clinic. If the fasting glucose remains outside of the allowed range, the subject must return to the site within the visit window and attempt the MMTT again.

An intravenous catheter can be placed in a patent vein in the subject's arm for the collection of blood samples. Insertion of the catheter should occur at least 30 minutes prior to any blood collections on the days MMTTs are performed. The subject should sit upright during the test. Slow walking is permitted, but vigorous exercise should be avoided.

Baseline, fasting blood samples are drawn for glucose and C-peptide within approximately five minutes prior to the start of the meal test. At time = 0, the subject drinks Boost $\mathbb{R}$  Hi-Protein (volume equal to 6 mL/kg body weight to a maximum of 360 mL). The entire drink must be ingested within 15 minutes.

For any visits requiring both an MMTT and an explant procedure, it is acceptable to perform the MMTT on a separate day up to 5 days prior to the explant procedure. Further details regarding MMTTs may be outlined in the study reference manual.

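### The SAP's second insulin-independence definition can rest on HbA1c and MMTT glucose measured while on injected insulin, and its criteria differ from the protocol's HbA1c <7.0% endpoint

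*SAP*

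**What the plan says.** SAP 4.6.6.2 defines exogenous insulin independence in two ways. The first is "having an exogenous insulin dose of 0 for a minimum of any 14 consecutive days during the study". The second keeps that condition and adds three limits: HbA1c ≤7.0%, MMTT fasting glucose ≤125 mg/dL and MMTT 120-minute glucose ≤180 mg/dL. The HbA1c and glucose used are "those values obtained at a clinic visit that is closest temporally to the 14 consecutive days of 0 exogenous insulin dose". The SAP accepts that the two may not belong together: "it is possible that the closest value temporally for HbA1c may be from a different clinic visit than the closest value temporally for glucose". It sets no direction and no maximum distance, and it does not mention insulin use at the chosen visit.

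Protocol 2.2.2 lists insulin independence and then "of those subjects achieving insulin independence, the percent achieving HbA1c <7.0" (percent). Protocol 10.4.5.1 states that "the percent of subjects who achieve exogenous insulin independence and an HbA1c < 7.0% will each be analyzed using Fisher's exact test". The Protocol Summary repeats the strict limit. None of these places has an MMTT glucose limit for this endpoint. The SAP's endpoint list (2.2.2) names insulin independence without the HbA1c clause. SAP 6.2 plans Fisher's exact test for "The number and percent of subjects who achieve exogenous insulin independence" under its own two definitions only.

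On the MMTT itself, Protocol 7.2 says "Basal exogenous insulin will be continued during the test"; only short-acting insulin is withheld, from four hours beforehand.

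**The concern.** The second definition is the one that combines freedom from insulin with good glycaemic control. It reads as though the control was observed while the subject was off insulin, but the matching rule does not secure this. If the nearest visit falls before insulin was stopped, the HbA1c reflects injected insulin, and the MMTT glucose may have been obtained with basal insulin running. If the nearest visit falls after insulin was resumed, a subject can be passed or failed on values that say nothing about the insulin-free period.

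The schedule makes this realistic. After implant, HbA1c is planned only at Weeks 16, 26, 52, 78 and 104. Protocol 7.10 expects insulin needs to fall gradually over three to six months, later in some subjects.

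The second issue is that the two documents describe different endpoints under one name, and the analysis plan covers only the SAP's.

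**Working it through.** The plan gives no figure to reproduce here, so the check is an enumeration of what the matching rule selects.

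**Inputs.** Target days are from SAP 4.3 and visit schedules from Table 1 of the protocol.
- HbA1c after implant: Days 113, 183, 365, 547, 729 (Weeks 16, 26, 52, 78, 104).
- MMTT from Week 16 on: Days 113, 141, 183, 274, 365, 456, 547, 638, 729.
- Run length L = 14 days, start day s from 113 to 715, which gives 715 − 113 + 1 = 603 positions.
- Distance is 0 if the visit falls inside the run, otherwise days from the nearer end of the run.

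**Formulas.** Between two consecutive visits G days apart, G − L run positions contain neither visit. For each such run the distances back and forward add up to G − L + 1.

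**HbA1c, L = 14.**
- Gap of 70 days (Day 113 to 183): 70 − 14 = 56 positions, 28 nearer the earlier visit and 28 nearer the later.
- Three gaps of 182 days: 182 − 14 = 168 positions each, 84 nearer the earlier visit and 84 nearer the later.
- Nearest value before the run: 28 + 3 × 84 = 280 of 603 (46%).
- Nearest value after the run: 28 + 3 × 84 = 280 of 603 (46%).
- Value inside the run: 603 − 560 = 43 (7%).
- Largest distance: the two distances sum to 182 − 14 + 1 = 169, so the smaller is at most 84 days.

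**MMTT, same positions.** A scheduled MMTT lies inside the run in 99 of 603: 1 for Day 113 and 14 for each of the seven visits from Day 141 to Day 638. The largest distance is (91 − 14 + 1)/2 = 39 days.

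**Examples.**
- Insulin stopped at Week 30, run on Days 211–224. HbA1c: Day 183 is 28 days before the run and Day 365 is 141 days after. MMTT: Day 183 is 28 days before and Day 274 is 50 days after. Both values come from Week 26, when the subject was still on insulin.
- Run on Days 323–336, insulin resumed on Day 337. Day 365 is 29 days after the run for both measures; the alternatives are 140 days before (HbA1c, Day 183) and 49 days before (MMTT, Day 274). Both values come from Week 52, after resumption.
- Run on Days 449–462. The HbA1c is from Day 365, 84 days before the run (Day 547 is 85 days after). The MMTT is from Day 456, inside the run.

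**Longer runs.** The number of positions in a 182-day gap with no HbA1c inside falls from 168 at L = 14 to 91 at L = 91 and 0 at L = 182. For HbA1c the problem therefore vanishes for runs of 182 days or more, provided distance is measured from the whole run. The SAP wording refers to the 14 days. If only the first 14 days counted, a long run beginning on Day 190 would still draw the Day 183 HbA1c, taken 7 days before it.

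**Criteria side by side.**

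| Subject meeting the 14-day condition | Protocol (HbA1c <7.0%) | SAP second definition |
|---|---|---|
| HbA1c exactly 7.0%, both glucose limits met | fails | passes |
| HbA1c 6.8%, 120-minute glucose 190 mg/dL | passes | fails |

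The protocol also uses two denominators: insulin-independent subjects in 2.2.2, and a joint percentage of subjects in 10.4.5.1.

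**The case against.** The strongest reply is that the counts are a worst case. They assume runs of exactly 14 days, equally likely positions and scheduled visits only. The definition sets 14 days as a minimum, durable responders will have visits inside their run, and Protocol 6.17 allows an MMTT at an unplanned visit. A value after the run is harmless if the subject is still off insulin. All of this stands. A reader might take 46%, or the 560 of 603 positions with no HbA1c inside the run, as the share of subjects who would be misclassified. The documents do not support that, because they give no distribution of run lengths or positions.

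A reader might also infer that the SAP altered the HbA1c criterion without recording it. That cannot be shown. The revision table covers changes after SAP version 1.0, which is not among the documents, and the SAP criterion may date from then. Protocol Section 10 lets the SAP modify the protocol, with an amendment for major endpoint changes. What can be shown is that the current texts disagree.

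It is fair, too, that the protocol states no timing rule for the HbA1c and nowhere says that this endpoint must show control by the graft alone. The planned listings of insulin dosing and MMTT results would let a reader check part of the matching afterwards. Neither point makes the summary percentage interpretable as written.

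Finally, requiring values inside the run would fail many subjects because of visit timing alone. That is a valid warning about the remedy, and the fix allows for it.

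**Conclusion.** The concern holds in two parts. First, the matching rule permits an HbA1c or MMTT glucose obtained on exogenous insulin to decide the second definition, in either direction. For exact 14-day runs on target days, the nearest HbA1c is before the run in 280 of 603 positions, after it in 280 and inside it in 43, up to 84 days away. The before-run positions are the clearer problem; the after-run positions matter only where insulin was resumed. The exposure shrinks as runs lengthen.

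Second, the SAP criterion (≤7.0% with two glucose limits) is not the protocol criterion (<7.0% alone), and no planned SAP analysis yields the latter. The inequality alone changes only a value of exactly 7.0%; the glucose limits can change more. The passages must be reconciled.

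The reach is limited to one of two definitions of one secondary endpoint, whose p-values are declared descriptive. The first definition and the primary C-peptide endpoint are unaffected. The change should be made because insulin independence with good control is a result that readers will take at face value.

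**What to change.** In SAP 4.6.6.2:

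1. Accept an HbA1c or MMTT glucose value only if it was measured during the zero-insulin run, or after it with a recorded zero dose on every day from the start of the run to the measurement. Blank diary days do not count as zero, as the SAP already states.
2. Do not count subjects who meet the first definition but have no qualifying value as meeting the second. Report their number separately as having no qualifying value, so that visit timing is not read as failed control.
3. Report the protocol criterion, insulin independence plus HbA1c <7.0%, both jointly and as a percent of insulin-independent subjects. Label the version with glucose limits as an additional SAP definition, and reconcile the HbA1c limit between the documents.

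The cost is SAP wording and a programming change that uses the existing insulin log; no new assessments are needed. The downside is that fewer subjects can meet the second definition. The change also does not remove every carry-over: an HbA1c drawn early in a run still partly reflects earlier glycaemia.
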